## 6. Provisions to Protect the Privacy Interests of Subjects:

### Confidentiality

- A. Protection of subject privacy. Information about study subjects will be kept confidential and managed according to the requirements of the Health Insurance Portability and Accountability Act of 1996 (HIPAA). To preserve patient confidentiality, study subjects will be assigned code numbers. Using these codes, none of the collection forms will contain the names or medical record number of the participants or other personal identifiers. There will be a master list at each institution matching the names of the participants to the code numbers. The list will be safely stored in a separate REDCap project. Paper-based consent and HIPAA documents will be stored in locked cabinets within locked offices, separate from the master lists. All electronic data will be stored on mainframe servers, and terminals and Tablet PCs will be password protected and maintained in locked offices.
- B. Database protection. Participant information will only be accessible to the PI, project manager, data analysts and research coordinators associated with the research. Data collected on Mt. Sinai computer servers and recording devices will be uploaded on a daily basis to mainframe servers supported by the local institutions. These data will lack personal identifiers other than a study identification code. Following the upload, the data on the recording devices and will be deleted. Encrypted data from the Northwestern site will be stored electronically in the Mount Sinai REDCap servers, which will serve as the data coordinating center, on a weekly basis. The transferred data will be free of personal data that qualifies as PHI. All data received at the data coordinating center (Mount Sinai) will be entered into a computerized database and stored in encrypted files on a mainframe server that is backed up nightly by the Mount Sinai Hospital IT Department.
- C. Confidentiality during adverse event reporting. Adverse event reports and annual summaries will not include subject-identifiable material. Each will include the coded identification number only.

To ensure that subjects feel at ease throughout the interviews and intervention sessions, the research personnel will remind the subjects that if at any point he/she becomes frustrated or does not wish to answer a particular question, he/she does not have to do so. In addition, the research personnel will give opportunities for breaks throughout the interviews and sessions.

## 7. Economic Impact on Subjects:

	Protocol Name:	Comprehensive Home-based Self-management Support for COPD Patients
	Principal Investigator:	[name], MPH
	Primary Contact Name/Contact Info:	[name]; [contact]; [contact]
	Date Revised:	4/16/21
	Study Number:	STUDY-18-01345

## 8. Payments/Reimbursements to Subjects:

If participants agree to take part in this research study, they will be paid for time and effort to participate in the research interviews. They will not be paid for intervention or control activities, and thus will not be paid for visits with the community health worker, pharmacist, or clinician, or visits with the research coordinator to review the COPD educational booklet.

For research interviews, a participant may receive up to \$255 for participating in this study. A participant will be paid \$65 after the completion of the each interview. If all 3 interviews are completed, participants will be paid a total of \$195. Up to an additional \$20 will be given to subjects after every interview once they return the electronic monitoring device for the medication (\$10) and an accelerometer (\$10). Participants will be paid in cash or money order at the completion of each interview. Payments will be for the research interviews only.

## 9. Consent Process:

### Setting:

Consent will take place in a private room in the Center for Advanced Medicine at Mount Sinai Hospital or over the phone

### Process:

Only members of the research team who have been fully trained in the protocol will obtain the treating provider's permission to recruit potential patients.

Subjects will be informed about the nature of the study by a CITI certified RC and asked to provide informed consent, including HIPAA authorization. They will be informed that their care at Mount Sinai or Northwestern Medicine will not be affected in any way if they decline to participate in the study. Additionally they will be notified that only those contents of their medical record that are necessary to evaluate the effectiveness of the intervention will be released to the research team at Mount Sinai (all phases) or Northwestern University (phase 1 only). The patients will complete a written informed or verbal consent document and will be given a copy of the consent document. They will be informed that they may withdraw from the study at any time and given contact information for the PI and study coordinator.

Once the investigator/RA is convinced that the subject verbally demonstrates understanding and agrees to the process, the consent is signed by the subject and/or the research delegate.

	Protocol Name:	Comprehensive Home-based Self-management Support for COPD Patients
	Principal Investigator:	[name], MPH
	Primary Contact Name/Contact Info:	[name]; [contact]; [contact]
	Date Revised:	4/16/21
	Study Number:	STUDY-18-01345

Individuals authorized to obtain written consent are the principal investigator, co-investigators, and RAs specifically designated by the principal investigator to work on this project.

Before including a patient in the study, the investigator or research assistant will verify that the given consent documents are written in the language that the subjects can understand them. Also the investigator or research assistant will verify that the subjects understand the objectives of the study, the type of information that will be collected, when and how it will be collected, and that participation in this study is voluntary. This will be done by asking the patient to describe to us what they understand the study entails and also to state the potential risks and benefits of the study.

**Non-English Speaking Subjects (See PPHS policy)**

Spanish.

Subjects who speak Spanish will be enrolled in the study by a Spanish-speaking RA. The consenting process for Spanish speaking participants is identical to the process for English speaking participants. All research materials (consent form, recruitment letter, recruitment script and survey) will be translated to Spanish. Only English and Spanish participants are permitted to participate because there are not enough personnel resources to accommodate adding more languages.

**Waiver or Alteration of the Consent Process**

The waiver of informed consent that is being requested is for a research report query from the data warehouse. This will allow the research staff to identify potentially eligible adults being seen in the Mount Sinai Health System.

**How the Research Involves No More Than Minimal Risks to Participants**

The database will be password protected and study subjects will be assigned a study ID number to protect the subject's identifiers. Study subjects will be identified by their ID numbers moving forward. Potential subjects who are not interested in participating will not be enrolled in the study.

**How the Waiver / Alteration Will Not Adversely Affect the Rights and Welfare of Participants**

We are requesting the minimal information to identify potential participants that will be stored in a password protected database. This information will not be released and information about potential participants and their unique IDs will not be linked in any other place.

	Protocol Name:	Comprehensive Home-based Self-management Support for COPD Patients
	Principal Investigator:	[name], MPH
	Primary Contact Name/Contact Info:	[name]; [contact]; [contact]
	Date Revised:	4/16/21
	Study Number:	STUDY-18-01345

Why It Is Not Practical To Conduct this Research Without a Waiver or Alteration of Informed Consent

This information is needed to recruit patients from the data warehouse housed at Mount Sinai Hospital (MSH). We would be unable to recruit these patients without access to this information. No further information about the patient will be collected unless we get research consent from the patient. We propose to use this information as there is no other way to ensure a representative patient sample.

Plans for Providing Participants with Additional Pertinent Information After Participation Where Appropriate

Results will not be communicated with study participants as part of the study is not to influence decision making. However, if the physician has a concern about the health or well-being of a participant (especially in reference to the clinical trial) then the physician will ask the participant's permission to discuss with the participant's physician or another provider.

**10. Process to Document Consent in Writing:**

Informed consent is obtained by the following process:

- Subject reviews the study consent form.
- The PI or RAs speak with the subject to review the consent, confirm subject's understanding, and answer any questions.
- Once the investigator/RA is convinced that the subject verbally demonstrates understanding and agrees to the process, the consent is signed by the subject and/or the research delegate. Individuals authorized to obtain written consent are the principal investigator, co-investigators, and RAs specifically designated by the principal investigator to work on this project.

For any subject being consented via phone we will follow the following procedure:

- Send the approved phone consent authorization to the prospective research subject for review.
- Arrange for a conversation between the participant and an authorized member of the research team to allow for full discussion of the combined consent/authorization. If verbal consent is obtained, collect identifiable data as applicable.
- If there is an adult witness on the phone at the time of the initial verbal consent, the documents will not be returned.

	Protocol Name:	Comprehensive Home-based Self-management Support for COPD Patients
	Principal Investigator:	[name], MPH
	Primary Contact Name/Contact Info:	[name]; [contact]; [contact]
	Date Revised:	4/16/21
	Study Number:	STUDY-18-01345

- If there is no adult witness to the phone consent/authorization, the written document will be requested to be returned via regular mail, fax, or email. If after two weeks, the signed document is not returned the data will be stripped of all identifiers and links such that the de-identified data are permanently anonymized.

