**Study Duration:**

The anticipated duration of participation will be 9 months. Participants will be participate in the intervention or control group for 6 months. Participants will complete a consent form at the time of enrollment and complete the baseline interview. The participant will complete 6 month and 9 month follow-up interviews.

We have allotted 24 months to recruit and enroll all participants.

	Protocol Name:	Comprehensive Home-based Self-management Support for COPD Patients
	Principal Investigator:	[name], MPH
	Primary Contact Name/Contact Info:	[name]; [contact]; [contact]
	Date Revised:	4/16/21
	Study Number:	STUDY-18-01345

We anticipate 12 additional months to finish preliminary analysis. The estimated date to complete analysis is the end of April 2022.

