Research Recruitment and Study Arm Assignment: We will identify potentially eligible patients and will obtain permission from the physician to recruit their patient. We will send a letter to the patient describing the study. One week later, the RA will phone the patient to answer questions and check eligibility of the participant. Eligible patients will be scheduled for an in-person or phone baseline interview, consented and enrolled in the study. We will assess the participant's inhaler technique, electronic medication adherence, and physical activity through a wearable activity monitor. The data from the electronic medication adherence device is for research purposes only. There are no studies demonstrating that providing such data to patients or their doctors improves their medication adherence, thus providing these data to them is unwarranted. The participant will then be randomized to the intervention or control arm.

B.3) SaMBA-COPD Intervention.

	Protocol Name:	Comprehensive Home-based Self-management Support for COPD Patients
	Principal Investigator:	[name], MPH
	Primary Contact Name/Contact Info:	[name]; [contact]; [contact]
	Date Revised:	4/16/21
	Study Number:	STUDY-18-01345

Step 1: Outreach and Engagement. The project manager will notify the CHW supervisor when an eligible and consented patient is randomized to receive care the intervention and will provide the patient's name and contact information (see Description of Procedures Being Performed for recruitment and randomization). The CHW will call the patient within 7 days of consent to schedule a home visit. The CHW will encourage caregivers to join all meetings.

Step 2: Intake. The CHW will perform an intake interview that includes collection of basic information about the patient and their health and healthcare, including medications, intended to enable them to understand their health problems and provide them with chronic illness self-management support.

Step 3: Symptom assessment, medication adherence, and inhaler technique. The CHW will assess the patients' symptoms, adherence to medications, and check inhaler technique following a standardized protocol, and correct errors in inhaler use if identified.

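### Allocation does not wait for documented phone consent, so the two-week unlinking rule could reach a patient who has already been randomised

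*Protocol*

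**What the plan says.** **Consent by phone.** Protocol section 9 (Setting) allows consent by phone, and its Process paragraph accepts either form: "The patients will complete a written informed or verbal consent document and will be given a copy of the consent document". Section 10 gives the phone procedure. Collection can begin on verbal agreement: "If verbal consent is obtained, collect identifiable data as applicable". With an adult witness on the line, nothing has to come back. Without one: "If there is no adult witness to the phone consent/authorization, the written document will be requested to be returned". Then: "If after two weeks, the signed document is not returned the data will be stripped of all identifiers and links". The same sentence makes this permanent.

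**Allocation.** Section 3(e), Description of Procedures Being Performed, item e, places randomisation directly after completion of the baseline interview, through REDCap, and names no other condition. The paragraph on recruitment and study arm assignment gives the order: "Eligible patients will be scheduled for an in-person or phone baseline interview, consented and enrolled in the study", then device and inhaler assessments, then "The participant will then be randomized to the intervention or control arm". Item g also allows the baseline interview by phone. Item c describes it as in person only.

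**After allocation.** Step 1 of the intervention (B.3) reads: "The project manager will notify the CHW supervisor when an eligible and consented patient is randomized to receive care the intervention". The community health worker (CHW) then calls no later than 7 days after consent.

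**Analysis.** Item j commits to intention-to-treat, with primary outcomes at 9 months. The SAP uses a difference-in-differences model with repeated measures. Neither mentions unlinked records.

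**The concern.** A patient removed before randomisation does no harm to the comparison of arms. A patient removed afterwards does. Section 10 and item e each read sensibly alone, but together they let an administrative rule act on someone who already has an allocation. By then the patient may know the arm and may have spoken to the CHW, so return of a form could in principle differ between arms.

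The step cannot be undone at analysis. Section 3(g) stores data under a study code, with the list matching codes to names kept separately. Once that link is gone, nothing collected at 6 or 9 months can be joined to the baseline record. The documents do not say whether the arm label stays with the stripped record, whether follow-up stops, or how the patient is counted under intention-to-treat.

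**Working it through.** **1. Does any passage hold allocation back?**

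- Study Duration: "Participants will complete a consent form at the time of enrollment and complete the baseline interview". This does not require an unwitnessed phone form to be back, and section 9 accepts a verbal consent document.
- B.3 Step 1 speaks of a consented patient. Under sections 9 and 10 a patient can be consented verbally and still be subject to the two-week rule.
- Item c (in-person baseline) would give an opportunity to take a signature first, but it does not require one, and the recruitment paragraph and item g allow the phone.
- Section 3(j) on withdrawal covers patients who ask to leave or whom the investigator removes. It does not cover a patient who stays in but returns no form.

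None of these makes allocation depend on documented consent.

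**2. Timing.** Section 10 does not say when the two weeks begin. Assume they begin at verbal consent (day 0), and that consent in Step 1 means the same event.

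- Unlinking: day 14.
- CHW call: by day 7. The call follows allocation, so it can be on time only if allocation is by day 7.
- Gap between allocation and unlinking: at least 14 − 7 = 7 days. With a same-day baseline it is 14 days.
- If the two weeks begin later, for example when the form is sent out, the gap is longer.
- If the baseline interview ends more than 14 days after consent, the rule acts first and the problem does not arise.

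One reading would avoid the overlap. The adherence devices run for 4 weeks after each interview (Description of Data, Adherence), and the recruitment paragraph lists adherence assessment before randomisation. If allocation waited for those 28 days, unlinking at day 14 would come first. That does not fit item e or the 7-day call.

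**3. Size.** The plan's numbers agree: 2 × 29 = 58. The documents do not say how many phone consents are unwitnessed or how many forms fail to come back.

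- One patient: 1/58 = 1.7% of the sample and 1/29 = 3.4% of an arm.
- Three patients: 3/58 = 5.2%, and 3/29 = 10.3% if all are in one arm.

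**4. Precision if the patient is lost.** Take an outcome with SD 1 and baseline-to-9-month correlation r, with n₁ and n₂ complete pairs per arm. The 95% half-width for the difference-in-differences is 1.96 × √[2(1 − r)(1/n₁ + 1/n₂)]. The value r = 0.5 is my assumption.

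| Pairs per arm | Half-width (SD units) | Change |
|---|---|---|
| 29 v 29 | 1.96 × √(1/29 + 1/29) = 0.515 | none |
| 29 v 28 | 1.96 × √(1/29 + 1/28) = 0.519 | +0.9% |
| 29 v 26 | 1.96 × √(1/29 + 1/26) = 0.529 | +2.8% |

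With 29 v 29 the half-width is 0.609 at r = 0.3 and 0.399 at r = 0.7. The factor 2(1 − r) cancels in the ratio, so the percentage changes do not depend on r. I give no figure for keeping an unlinked patient's records as unpaired observations. It would depend on a working correlation that the SAP does not state, and on follow-up that no passage describes.

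**The case against.** **The text is incomplete.** The application form says it must be read with a protocol, and the consent pages were removed before review. The phone consent authorisation may say what happens when a form is not returned. This stands: the absence of a rule can be claimed only for the visible text.

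**Several conditions must coincide.** They are phone consent, no witness, no returned form, a clock starting near consent, and allocation within two weeks. This also stands, and is why the number may be zero. A reader might infer that patients were in fact lost, or that the result is biased in a known direction. The documents give no rates and no sign of either.

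**The result resembles ordinary early dropout.** Two weeks after consent little beyond baseline exists, and stripping names and links need not delete the coded record or its arm. This stands in part. A reader might infer that the rule erases the allocation, but section 3(g) does not say so. The opposite inference, that unlinked patients would be followed and simply analysed unpaired, has no support either. The difference from dropout is that the plan's own rule causes the loss after allocation, and it can be avoided.

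**Item c describes an in-person baseline.** True, but it conflicts with the recruitment paragraph and item g. That calls for reconciliation and does not settle the matter.

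**Conclusion.** The gap is real in the visible text, and it is minor. Allocation follows the baseline interview with no check that phone consent is documented, while an unwitnessed, unreturned consent leads to permanent unlinking after two weeks. If the two weeks run from about the time of consent, and allocation happens within them, a randomised patient can be unlinked and would probably be lost from the intention-to-treat comparison.

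The precision cost is small: about 0.9% on the interval for one patient and 2.8% for three in one arm. The SAP itself says the trial was not powered for outcome differences. What matters is who is counted after randomisation. The conclusion rests on the assumed start of the clock and on the removed consent pages containing no rule that closes the gap.

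**What to change.** **If patients are still being enrolled:**

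1. Amend item e so that REDCap opens randomisation only when the baseline interview is complete and consent is documented by in-person signature, witnessed phone consent, or receipt of the signed form. The two-week rule then acts only before allocation.
2. State in section 10 when the two weeks start.
3. Reconcile the recruitment paragraph and items c, e and g on whether baseline may be by phone, and reconcile Step 1 with them on how the CHW call is timed relative to consent and allocation.

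The cost is a few sentences and one REDCap condition. The downside is up to about two weeks between baseline and allocation, for unwitnessed phone consents only.

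**If enrolment is complete**, as the past tense of the SAP (dated 9-06-2021) suggests it may be: count every randomised patient from the REDCap allocation log in the intention-to-treat set. Report by arm, including zero, how many were unlinked under section 10 and whether any of their data could be used. The log should be the source because the stripped record may not carry the arm. This costs one sentence in the SAP and one line in the participant flow.

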## 11. Vulnerable Populations:

- a) Unless already detailed in the protocol, please indicate which of the following populations are either included or excluded in this project: Indicate specifically whether you will include (target) or exclude each of the following populations:

Include	Exclude	Vulnerable Population Type
	X	Adults unable to consent
	X	Individuals who are not yet adults (e.g. infants, children, teenagers)
	X	Wards of the State (e.g. foster children)
	X	Pregnant women
	X	Prisoners

Based on the demographics of the communities served by Mount Sinai and the characteristics of our prior COPD studies, we expect that women will comprise approximately 60% of enrolled subjects, Hispanics approximately 40% to 45%, and Black, non-Hispanic 30% to 35%. The proportion of women and minorities in this population is in accordance with the epidemiology of COPD in these communities.

## 12. Multi-Site Human Research:

[name] will be responsible for overseeing data collection activities and quality of data collected. For the research study (Aims 1-2), we selected validated tools and electronic measures that are known to be highly valid and reliable. Data will be collected using paper handouts and then entering the data onto our Redcap with built in logic patterns to minimize data entry errors. [name] will train research coordinators in survey administration techniques. We will also conduct random checks of 10% of all collected data to assess for data entry errors, ranges of

	Protocol Name:	Comprehensive Home-based Self-management Support for COPD Patients
	Principal Investigator:	[name], MPH
	Primary Contact Name/Contact Info:	[name]; [contact]; [contact]
	Date Revised:	4/16/21
	Study Number:	STUDY-18-01345

input values, missing data, and overall data quality. Study team members will meet monthly to review progress in recruitment goals, review preliminary results, and identify and resolve emerging problems.

- a) If coordinating center functions are taking place at Sinai, whether or not it is also a clinical site, please answer the following with appropriate justification and documentation, if needed:
- (i) Are the management, data analysis, and Data Safety and Monitoring (DSM) systems adequate, given the nature of the research involved?  
  
YES
  - (ii) Is the sample protocols and informed consent documents developed and distributed to each collaborating institution?;  
  
YES
  - (iii) Does each collaborating institution hold an applicable OHRP-approved Assurance?;  
  
YES
  - (iv) Will each protocol be reviewed and approved by the IRB at the collaborating institution prior to the enrollment of subjects?;  
  
YES
  - (v) Have all substantive modifications by the collaborating institution to the sample consent, especially related to risks or alternative procedures, been appropriately justified?;  
  
YES
  - (vi) Will informed consent be obtained from each subject in compliance with HHS regulations?  
  
*If this is a multi-site study where you are the lead investigator, describe the management of information (e.g., results, new information, unanticipated problems involving risk to subjects or others, or protocol modifications) among sites to protect subjects.*  
  
YES

	Protocol Name:	Comprehensive Home-based Self-management Support for COPD Patients
	Principal Investigator:	[name], MPH
	Primary Contact Name/Contact Info:	[name]; [contact]; [contact]
	Date Revised:	4/16/21
	Study Number:	STUDY-18-01345

